6.3.1.4 Non-Target Lesions

All other lesions (or sites of disease) including any measurable lesions over and above the 5 target lesions should be identified as **non-target lesions** and should also be recorded at baseline. Measurements of these lesions are not required, but the presence, absence, or in rare cases unequivocal progression of each should be noted throughout follow-up.

6.3.2 Methods of Evaluation of Measurable Disease

6.3.2.1 Guidelines for Evaluation of Measurable Disease

All measurements should be taken and recorded in metric notation using a ruler or calipers. All baseline evaluations should be performed as closely as possible to the beginning of treatment and never more than 4 weeks before the beginning of the treatment.

The same method of assessment and the same technique should be used to characterize each identified and reported lesion at baseline and during follow-up. Imaging-based evaluation is

preferred to evaluation by clinical examination unless the lesion(s) being followed cannot be imaged but are assessable by clinical exam.

6.3.2.2 Metastatic Bone Lesions

Disease progression is considered if any new lesion is observed on bone scan. New lesions seen by the end of Cycle 2 or before Cycle 3 (with the first re-staging bone scan) may represent disease that was not detected on the pre-study scan, and a confirmatory scan will be required at the next scheduled re-staging bone scan unless clinically not indicated. If confirmed, progression should be dated by the initial time when the lesions are first detected. If new lesions are seen after Cycle 2, but no additional lesions are seen on confirmatory scans, the scans from post-Cycle 2 would serve as the baseline scan to evaluate for disease progression (80).

6.3.2.3 Clinical Lesions

Clinical lesions will only be considered measurable when they are superficial (e.g., skin nodules and palpable lymph nodes) and ≥ 10 mm diameter as assessed using calipers (e.g., skin nodules). In the case of skin lesions, documentation by color photography, including a ruler to estimate the size of the lesion, is recommended.

6.3.2.4 Methods of Measurement

Chest X-ray - Lesions on chest x-ray are acceptable as measurable lesions when they are clearly defined and surrounded by aerated lung. However, CT is preferable.

CT and MRI - CT and MRI are the best currently available and reproducible methods to measure target lesions selected for response assessment. For this study helical Multi-detector CT will be performed with cuts of 5 mm in slice thickness for chest, abdomen and pelvis lesions and 2-3 mm thickness for head and neck lesions.

6.3.2.5 Additional response evaluation using volumetric analysis

In addition, the utility of volumetric tumor measurement in patients with measurable disease will be prospectively evaluated and compared to 1D and 2D measurements.

6.3.3 Response Criteria for Radiographic Studies

6.3.3.1 Measuring of Soft Tissue Disease

a. Evaluation of Target Lesions

Complete Response (CR)

Disappearance of all target lesions. Any pathological lymph nodes (whether target or non-target) must have reduction in short axis to < 10 mm.

Partial Response (PR)

At least a 30% decrease in the sum of the diameters of target lesions, taking as reference the baseline sum diameters.

Progressive Disease (PD)

At least a 20% increase in the sum of the diameters of target lesions, taking as reference the smallest sum on study (this includes the baseline sum if that is the smallest on study). In addition to the relative increase of 20%, the sum must also demonstrate an absolute increase of at least 5 mm. (Note: The appearance of one or more new lesions is also considered progressions.)

Note: For this study, determination of PD will not be made prior to the Day 60 evaluation.

Stable Disease (SD)

Neither sufficient shrinkage to qualify for PR nor sufficient increase to qualify for PD, taking as reference the smallest sum diameters while on study.

b. Evaluation of Non-Target Lesions

Complete Response (CR)

Disappearance of all non-target lesions and normalization of tumor marker level. All lymph nodes must be non-pathological in size (<10 mm short axis).

Note: Tumor markers alone cannot be used to assess response. If tumor markers are initially above the upper normal limit, they must normalize for a patient to be considered in complete clinical response.

Non-CR/Non-PD (Stable Disease, SD)

Persistence of one or more non-target lesion(s) and/or maintenance of tumor marker level above the normal limits.

Progressive Disease (PD)

Appearance of one or more new lesions and/or *unequivocal progression* of existing non-target lesions. *Unequivocal progression* should not normally trump target lesion status. It must be representative of overall disease status change, not a single lesion increase.

Although a clear progression of “non-target” lesions only is exceptional, the opinion of the treating physician should prevail in such circumstances, and the progression status should be confirmed at a later time by the review panel (or Principal Investigator).

c. Evaluation of Best Overall Response

The best overall response is the best response recorded from the start of the treatment until disease progression/recurrence (taking as reference for progressive disease the smallest measurements recorded since the treatment started). The patient's best response assignment will depend on the achievement of both measurement and confirmation criteria.

For Patients with Measurable Disease (i.e., Target Disease)

Target Lesions	Non-Target Lesions	New Lesions	Overall Response	Best Overall Response when Confirmation is Required*
CR	CR	No	CR	≥4 wks. Confirmation**
CR	Non-CR Non-PD	No	PR	≥4 wks. Confirmation**
CR	Not evaluated	No	PR	
PR	Non-CR Non-PD Not evaluated	No	PR	

Target Lesions	Non-Target Lesions	New Lesions	Overall Response	Best Overall Response when Confirmation is Required*
SD	Non-CR Non-PD Not evaluated	No	SD	Documented at least once ≥4 wks. from baseline**
PD	Any	Yes or No	PD	No prior SD, PR or CR
Any	PD***	Yes or No	PD	
Any	Any	Yes	PD	

*See RECIST 1.1 manuscript for further details on what is evidence of a new lesion.
 
**Only for non-randomized trials with response as primary endpoint.
 
***In exceptional circumstances, unequivocal progression in non-target lesions may be accepted as disease progression.
				

- d. Patients with a global deterioration of health status requiring discontinuation of treatment without objective evidence of disease progression at that time should be reported as “*symptomatic deterioration.*” Every effort should be made to document the objective progression even after discontinuation of treatment.
- e. In some circumstances, it may be difficult to distinguish residual disease from normal tissue. When the evaluation of complete response depends on this determination, it is recommended that the residual lesions be investigated (fine needle aspirate/biopsy) before confirming the complete response status.

6.3.4 Confirmatory Measurement/Duration of Response

- Confirmation

To be assigned a status of PR or CR, changes in tumor measurements must be confirmed by repeat assessments that should be performed at least 4 weeks after the criteria for response are first met.

- Duration of Overall Response

The duration of overall response is measured from the time measurement criteria are met for CR or PR (whichever is first recorded) until the first date that recurrent or progressive disease is objectively documented (taking as reference for progressive disease the smallest measurements recorded since the treatment started).

The duration of overall CR is measured from the time measurement criteria are first met for CR until the first date that progressive disease is objectively documented.

6.4 TOXICITY CRITERIA

The following adverse event management guidelines are intended to ensure the safety of each patient while on the study. The descriptions and grading scales found in the revised NCI Common Terminology Criteria for Adverse Events (CTCAE) version 5.0 will be utilized for AE reporting.

All appropriate treatment areas have access to a copy of the CTCAE version 5.0. A copy of the CTCAE version 5.0 can be downloaded from the CTEP web site (http://ctep.cancer.gov/protocolDevelopment/electronic_applications/ctc.htm).

7 NIH REPORTING REQUIREMENTS/DATA AND SAFETY MONITORING PLAN

7.1 DEFINITIONS

Please refer to definitions provided in Policy 801: Reporting Research Events found [here](#).

7.2 OHSRP OFFICE OF COMPLIANCE AND TRAINING/IRB REPORTING

7.2.1 Expedited Reporting

Please refer to the reporting requirements in Policy 801: Reporting Research Events and Policy 802: Non-Compliance Human Subjects Research found [here](#). Note: Only IND Safety Reports that meet the definition of an unanticipated problem will need to be reported per these policies.

7.2.2 IRB Requirements for PI Reporting Continuing Review

Please refer to the reporting requirements in Policy 801: Reporting Research Events found [here](#).

7.2.3 NCI Clinical Director Reporting

Problems expeditiously reported to the OHSRP in iRIS will also be reported to the NCI Clinical Director. A separate submission is not necessary as reports in iRIS will be available to the Clinical Director.

In addition to those reports, all deaths that occur within 30 days after receiving a research intervention should be reported via email to the Clinical Director unless they are due to progressive disease.

To report these deaths, please send an email describing the circumstances of the death to [name] at [contact] within one business day of learning of the death.

7.3 NIH REQUIRED DATA AND SAFETY MONITORING PLAN

7.3.1 Principal Investigator/Research Team

The clinical research team will meet on a weekly basis when patients are being actively treated on the trial to discuss each patient in detail. Decisions about dose level enrollment and dose escalation if applicable will be made based on the toxicity data from prior patients.

All data will be collected in a timely manner and reviewed by the principal investigator or a clinical associate investigator. Events meeting requirements for expedited reporting as described in Section [7.2.1](#) will be submitted within the appropriate timelines.

The principal investigator will review adverse event and response data on each patient to ensure safety and data accuracy. The principal investigator will personally conduct or supervise the investigation and provide appropriate delegation of responsibilities to other members of the research staff.

8 SPONSOR SAFETY REPORTING

8.1 DEFINITIONS

8.1.1 Adverse Event

Any untoward medical occurrence in a patient or clinical investigation subject administered a pharmaceutical product and which does not necessarily have a causal relationship with this treatment. An adverse event (AE) can therefore be any unfavorable and unintended sign (including an abnormal laboratory finding), symptom, or disease temporally associated with the use of a medicinal (investigational) product, whether or not related to the medicinal (investigational) product (ICH E6 (R2)).

8.1.2 Serious Adverse Event (SAE)

An adverse event or suspected adverse reaction is considered serious if in the view of the investigator or the sponsor, it results in any of the following:

- Death.
- A life-threatening adverse event (see Section [8.1.3](#)).
- Inpatient hospitalization or prolongation of existing hospitalization.
 - A hospitalization/admission that is pre-planned (i.e., elective or scheduled surgery arranged prior to the start of the study), a planned hospitalization for pre-existing condition, or a procedure required by the protocol, without a serious deterioration in health, is not considered a serious adverse event.
 - A hospitalization/admission that is solely driven by non-medical reasons (e.g., hospitalization for patient convenience) is not considered a serious adverse event.
 - Emergency room visits or stays in observation units that do not result in admission to the hospital would not be considered a serious adverse event. The reason for seeking medical care should be evaluated for meeting one of the other serious criteria.
- Persistent or significant incapacity or substantial disruption of the ability to conduct normal life functions.
- A congenital anomaly/birth defect.
- Important medical events that may not result in death, be life-threatening, or require hospitalization may be considered a serious adverse drug experience when, based upon appropriate medical judgment, they may jeopardize the patient or subject and may require medical or surgical intervention to prevent one of the outcomes listed in this definition.

8.1.3 Life-threatening

An adverse event or suspected adverse reaction is considered "life-threatening" if, in the view of either the investigator or sponsor, its occurrence places the patient or subject at immediate risk of death. It does not include an adverse event or suspected adverse reaction that, had it occurred in a more severe form, might have caused death. (21CFR312.32)

8.1.4 Severity

The severity of each Adverse Event will be assessed utilizing the CTCAE version 5.0.

8.1.5 Relationship to Study Product

All AEs will have their relationship to study product assessed using the terms: related or not related.

- Related – There is a reasonable possibility that the study product caused the adverse event. Reasonable possibility means that there is evidence to suggest a causal relationship between the study product and the adverse event.
- Not Related – There is not a reasonable possibility that the administration of the study product caused the event.

8.2 ASSESSMENT OF SAFETY EVENTS

AE information collected will include event description, date of onset, assessment of severity and relationship to study product and alternate etiology (if not related to study product), date of resolution of the event, seriousness and outcome. The assessment of severity and relationship to the study product will be done only by those with the training and authority to make a diagnosis and listed on the Form FDA 1572 as the site principal investigator or sub-investigator. AEs occurring during the collection and reporting period will be documented appropriately regardless of relationship. AEs will be followed through resolution.

SAEs will be:

- Assessed for severity and relationship to study product and alternate etiology (if not related to study product) by a licensed study physician listed on the Form FDA 1572 as the site principal investigator or sub-investigator.
- Recorded on the appropriate SAE report form, the medical record and captured in the clinical database.
- Followed through resolution by a licensed study physician listed on the Form FDA 1572 as the site principal investigator or sub-investigator.

For timeframe of recording adverse events, please refer to Section **6.1**. All serious adverse events recorded from the time of first investigational product administration must be reported to the Sponsor. Any exceptions to the expedited reporting requirements are found in Section **Error! Reference source not found.**

8.3 REPORTING OF SERIOUS ADVERSE EVENTS

Any AE that meets protocol-defined serious criteria or meets the definition of Adverse Event of Special Interest that require expedited reporting must be submitted immediately (within 24 hours of awareness) to OSRO Safety using the CCR SAE report form. Any exceptions to the expedited reporting requirements are found in Section **Error! Reference source not found.**

All SAE reporting must include the elements described in Section **8.2**.

SAE reports will be submitted to the Center for Cancer Research (CCR) at: [contact] and to the CCR PI and study coordinator. CCR SAE report form and instructions can be found at: <https://ccrod.cancer.gov/confluence/pages/viewpage.action?pageId=157942842>

Following the assessment of the SAE by OSRO, other supporting documentation of the event may be requested by the OSRO Safety and should be provided as soon as possible.

8.4 REPORTING PREGNANCY

8.4.1 Maternal Exposure

If a patient becomes pregnant during the course of the study, the study treatment should be discontinued immediately and the pregnancy reported to the Sponsor no later than 24 hours of when the Investigator becomes aware of it. The Investigator should notify the Sponsor no later than 24 hours of when the outcome of the Pregnancy becomes known.

Pregnancy itself is not regarded as an SAE. However, congenital abnormalities or birth defects and spontaneous miscarriages that meet serious criteria (Section 8.1.2) should be reported as SAEs.

The outcome of all pregnancies (spontaneous miscarriage, elective termination, ectopic pregnancy, normal birth, or congenital abnormality) should be followed up and documented.

8.4.2 Paternal Exposure

Male patients should refrain from fathering a child or donating sperm during the study and for 60 days after the last dose of mithramycin.

Pregnancy of the patient's partner is not considered to be an AE. However, the outcome of all pregnancies (spontaneous miscarriage, elective termination, ectopic pregnancy, normal birth, or congenital abnormality) occurring from the date of the first dose until 60 days after the last dose should, if possible, be followed up and documented.

8.5 REGULATORY REPORTING FOR STUDIES CONDUCTED UNDER CCR-SPONSORED IND

Following notification from the investigator, CCR, the IND Sponsor, will report any suspected adverse reaction that is both serious and unexpected in expedited manner to the FDA in accordance to 21 CFR 31.2.32. CCR will report an AE as a suspected adverse reaction only if there is evidence to suggest a causal relationship between the study product and the adverse event. CCR will notify FDA and all participating investigators (i.e., all investigators to whom the Sponsor is providing drug under its INDs or under any investigator's IND) in an IND safety report of potential serious risks from clinical trials or any other source, as soon as possible, in accordance to 21 CFR Part 312.32.

All serious events will be reported to the FDA at least annually in a summary format.

9 CLINICAL MONITORING

As a sponsor for clinical trials, FDA regulations require the CCR to maintain a monitoring program. The CCR's program allows for confirmation of: study data, specifically data that could affect the interpretation of primary and secondary study endpoints; adherence to the protocol, regulations, ICH E6 and SOPs; and human subjects protection. This is done through independent verification of study data with source documentation focusing on:

- Informed consent process
- Eligibility confirmation
- Drug administration and accountability
- Adverse events monitoring
- Response assessment.

The monitoring program also extends to multi-site research when the CCR is the coordinating center.

This trial will be monitored by personnel employed by an CCR contractor. Monitors are qualified by training and experience to monitor the progress of clinical trials. Personnel monitoring this study will not be affiliated in any way with the trial conduct.

10 STATISTICAL CONSIDERATIONS

The Phase 1 dose escalation study of mithramycin infusion will be conducted as a single arm study to minimize the number of patients needed to define MTD. Pharmacokinetic analyses, as well as analyses of molecular endpoints such as HDAC4, KIAA1199, PMAIP and p21 expression in tumor tissues and PBMC before and after treatment will be performed, with the primary focus being with respect to results at the MTD. It is anticipated that non-parametric statistical methods will be used to compare paired results before and after treatment (but not between groups), as well as to perform comparisons or correlations among parameters. As the exact set of comparisons and analyses to be performed will be determined following completion of the trial and will be based on limited numbers of patients, the analyses will be considered exploratory and hypothesis generating rather than definitive. As many as 15 patients may theoretically need to be accrued to define the MTD if the amended dose levels (DL-1 and DL-1A) each require 6 patients, in addition to the 3 subjects that were already enrolled at dose level DL1.

The primary endpoint of the Phase II component study will be evaluated for objective response by RECIST criteria v 1.1. Patients will be enrolled into two cohorts (primary thoracic malignancy; extra-thoracic malignancy metastatic to the chest). The best response to mithramycin will be examined for each cohort. In each cohort, the trial will seek to rule out an unacceptably low 5% objective response rate (ORR; $p_0=0.05$), in favor of a higher response rate of 30% ($p_1=0.30$). With $\alpha=0.10$ (probability of accepting a poor treatment=0.10) and $\beta=0.10$ (probability of rejecting a good treatment=0.10), the study will initially enroll 7 evaluable patients in each cohort and if 0 of the 7 have a response, then no further patients will be accrued in that cohort. If 1 or more of the first 7 in a cohort have a response, then accrual will continue until a total of 21 evaluable patients have enrolled in that cohort. As it may take several weeks to determine if a patient has experienced a response, a temporary pause in the accrual to the trial may be necessary to ensure that enrollment to the second stage is warranted. If there are 1 to 2 responses in 21 patients, this would be an uninterestingly low response rate, while if there were 3 or more responses in 21 patients, then this would be sufficiently interesting to warrant further study of the patients from that cohort in later trials. Under the null hypothesis (5% response rate), the probability of early termination in each cohort is 70%.

The following table summarizes the two stage design that will be used for each cohort in the Phase II component of this trial.

	Cumulative Number of Responses	Decision
Stage 1: Enter 7 patients	0	Terminate the trial: agent ineffective
	1 or more	Inconclusive result, continue trial (proceed to Stage 2)
Stage 2: Enter 14 additional patients	2 or less	Terminate the trial: agent ineffective
	3 or more	Terminate the trial: agent effective

With two cohorts, up to 42 evaluable patients may be required to be accrued to the Phase II portion. It is expected that 10-15 patients per year may enroll onto this study. Thus, 2 to 3 years may be needed to enroll up to 15 patients in Phase I plus 36 evaluable patients in Phase II (up to 6 patients may continue from the Phase I component of the trial). This may be completed much sooner depending on the number actually required. To allow for a small number of inevaluable patients, the accrual ceiling will be set at 60.

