10.2 EVALUATION OF RESPONSE

Any patient who is enrolled and receives at least one full course (4 cycles) of mithramycin will be considered evaluable for response provided: (1) the patient demonstrates progressive disease or death while on protocol therapy; (2) the patient is observed on protocol therapy for at least one course and the tumor is not removed surgically prior to the time complete response or partial response is confirmed; or (3) the patient demonstrates a complete or partial response as confirmed according to protocol criteria. Patients who electively terminate therapy before receiving completing a full course of mithramycin and do not expire within 14 days from start of treatment will be replaced. Patients who experience disease progression after the first course but who did not receive a full course will be taken off-treatment and will only be evaluable for toxicity (not evaluable for response).

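### Section 10's accrual period of 2 to 3 years does not follow from 51 patients at 10 to 15 a year, Section 2.4's Phase I maximum of 54 conflicts with Section 10's 15, and the carry-over of up to 6 Phase I patients has no written rule

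*Combined protocol and SAP*

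**What the plan says.** **Accrual.** Section 10 states: "It is expected that 10-15 patients per year may enroll onto this study". It continues: "Thus, 2 to 3 years may be needed to enroll up to 15 patients in Phase I plus 36 evaluable patients in Phase II". The next sentence adds: "This may be completed much sooner depending on the number actually required".

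**Phase I size.** Section 10 states: "As many as 15 patients may theoretically need to be accrued to define the MTD". This is 6 at each of the two amended dose levels plus the 3 patients already enrolled. Section 2.4 instead lets up to 54 Cohort 1 patients be assigned to Arm 1 before the MTD is determined.

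**Phase II size and carry-over.** Section 10 states: "With two cohorts, up to 42 evaluable patients may be required to be accrued to the Phase II portion". The 36 comes from a parenthesis: "up to 6 patients may continue from the Phase I component of the trial". The ceiling follows: "To allow for a small number of inevaluable patients, the accrual ceiling will be set at 60". Section 2.4 assigns up to 7 evaluable patients per Phase II cohort, then possibly 14 more, and does not mention carry-over. Section 3.1.2.2 speaks of 14 additional patients once the MTD is defined.

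**Evaluability.** Section 10.2 states: "Any patient who is enrolled and receives at least one full course (4 cycles) of mithramycin will be considered evaluable for response", subject to further conditions. It also says that patients who progress without a full course are not evaluable for response.

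**The concern.** Three planning figures that should agree do not.

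- The accrual period is presented as a consequence of the rate, yet it is shorter than the rate allows for the number of patients named.
- Two sections give different maxima for the same activity, determining the MTD. The larger one leaves no room for Phase II as planned.
- Carry-over changes how many new patients are needed and who enters the primary analysis, but it appears only in a parenthesis.

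The third item is the one that touches inference. Section 3.1.2.1 restages all Phase I patients after the fourth cycle, so some responses may be known before anyone decides who is carried over. Each cohort's first stage turns on a single response in 7 patients. An unwritten rule therefore leaves room for a choice made with outcomes in view.

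**Working it through.** **1. Accrual period.** Inputs from Section 10: 10 to 15 patients a year; 15 + 36 = 51 patients; stated period 2 to 3 years. Years = patients / annual rate.

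| Patients | At 15 a year | At 10 a year |
|---|---|---|
| 51 (15 + 36, as stated) | 3.4 | 5.1 |
| 48 (51 less the 3 already enrolled) | 3.2 | 4.8 |
| 57 (15 + 42, no carry-over) | 3.8 | 5.7 |
| 60 (ceiling) | 4.0 | 6.0 |

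The stated 2 to 3 years is not reproduced in any row. Three years at the fastest rate give 3 x 15 = 45 patients. Enrolling 51 in 2 to 3 years needs 51/3 = 17 to 51/2 = 25.5 a year. None of these durations includes the pause between stages that Section 10 foresees.

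Early stopping could shorten the trial. The expected size per cohort is 7 + 14 x (1 - (1 - p)^7), which is 11.22 at p = 0.05 and 19.85 at p = 0.30. With Phase I held at its maximum of 15, the total is 15 + 2n - k, where n is that size and k is the number carried over:

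| True response rate | k | Total | Years |
|---|---|---|---|
| 5% | 6 | 31.4 | 2.1 to 3.1 |
| 5% | 0 | 37.4 | 2.5 to 3.7 |
| 30% | 6 | 48.7 | 3.2 to 4.9 |
| 30% | 0 | 54.7 | 3.6 to 5.5 |

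So 2 to 3 years roughly describes an ineffective drug with early stopping. The sentence in Section 10 names 15 + 36.

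**2. Phase I maximum against the ceiling.** Section 10: 6 + 6 + 3 = 15. Section 2.4: 54. Ceiling: 60.

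- 60 - 54 = 6 places remain.
- First stage of both cohorts: 54 + 14 - 6 = 62 with full carry-over and 54 + 14 = 68 without.
- Full Phase II: 54 + 36 = 90 or 54 + 42 = 96.
- Largest Phase I that leaves room for full Phase II: 60 - 42 = 18 with 42 new patients, or 60 - 36 = 24 with 36 new.

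**3. Carry-over.** With 15 in Phase I and k evaluable patients carried over:

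- New Phase II patients = 42 - k.
- Total = 15 + 42 - k = 57 - k.
- Reserve for inevaluable patients = 60 - (57 - k) = 3 + k, so 9 if k = 6 and 3 if k = 0.

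The plan's 36 is therefore reached only if all 6 carry over.

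**4. Why selection would matter.** For the design of 0/7 then 2/21, the exact binomial calculation gives early stopping of 0.698 at a 5% rate (Section 10 states 70%), type I error of 0.064 and power of 0.904. Suppose one patient already known to have responded were placed in a cohort. Stage 1 would then pass automatically, and 2 or more responses among the other 20 would suffice. At a true 5% rate that probability is 1 - 0.95^20 - 20 x 0.05 x 0.95^19 = 1 - 0.358 - 0.377 = 0.26, against 0.064 by design. This is conditional on such a placement and is not an estimate of what will happen.

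**The case against.** **The timeline is hedged and of little consequence.** The text speaks of what may be needed, the shortfall at the closest ends is 0.4 year (0.2 without the 3 already enrolled), and early stopping can bring the trial near 3 years. The low weight is accepted. Early stopping does not rescue the figure, because the following sentence treats smaller numbers as a separate, faster case.

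**54 is only a cap.** A reader might infer that it breaches the ceiling. It does not: 54 is below 60, and the current escalation rules lead to 15. The conflict is with Section 10 and with the space left for Phase II.

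**Section 2.4 permits carry-over.** A reader might infer that it requires 42 new patients. It says up to 7 per cohort, so carried patients could fill places. Only Section 3.1.2.2 reads against carry-over.

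**Outcomes may not be known in time.** The MTD is judged on cycle 1 and restaging follows cycle 4, so responses at the last dose level tested may be pending when Phase II opens. That is fair, but no section fixes when the choice is made. A reader might also infer that responders will be picked. Nothing in the documents says so; the point is the missing safeguard.

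**The intended rule is obvious.** Six equals the most patients that one amended dose level can hold, and tumour origin gives the cohort. This is a reasonable inference, but Section 3.1.2.1 reports that two of the first three patients continued at the DL-1 dose after reduction. If DL-1 became the MTD, up to 8 Phase I patients would have received that dose. Limiting carry-over to patients evaluable under Section 10.2 would not be neutral either, since completing a course depends partly on outcome.

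**Conclusion.** The point holds in three parts of unequal weight.

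- The accrual period is wrong for the numbers it cites: 3.4 to 5.1 years, not 2 to 3. This assumes the stated rate and no pause. It is minor and has no effect on the error rates.
- The Phase I maxima of 54 and 15 contradict each other, and 54 cannot be combined with the first stage of both Phase II cohorts under the ceiling of 60.
- The carry-over lacks a rule. It shifts the number of new Phase II patients between 36 and 42 and the reserve between 9 and 3, and it leaves the primary analysis open to selection on known response.

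A reader might go further and conclude that the two-stage design or the ceiling is faulty. The documents do not support that: type I error is 6.4% and power 90.4%, within the stated 10% limits, and with 15 in Phase I the ceiling of 60 covers even the 57 patients needed without carry-over.

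**What to change.** **Section 10, accrual.** State about 3.4 to 5.1 years for 51 patients (3.8 to 5.7 for 57; 4 to 6 at the ceiling), before any pause, or justify a faster rate. If an early-stopping figure is added, give its assumed response rate and carry-over, and label it as holding Phase I at its maximum of 15.

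**Section 2.4, Phase I.** Reconcile the 54 with the 15 in Section 10 and with the ceiling, under which Phase I can be at most 18 (42 new Phase II patients) or 24 (36 new).

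**Sections 2.4, 3.1.2.2 and 10, carry-over.** State one rule, fixed before Phase I responses are used. There are two options:

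- All Phase I patients whose assigned starting dose was the level declared the MTD count, in the cohort of their tumour origin and from stage 1. They follow the same evaluability and replacement rules as Phase II patients, with no selection on known response.
- No Phase I patients count.

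Say whether the two patients who continued at the DL-1 dose after reduction are included. Give the matching number of new patients (42 - k) and reserve (3 + k).

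**Cost.** Text changes only; the Simon design and the ceiling are unchanged. The stated timeline lengthens. If none are carried over, up to 6 more new patients are needed within the ceiling, and the reserve falls from 9 to 3.
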